3.1.4 Efficacy

Onsite/in-clinic assessments will be scheduled around the second (PM) study daily treatment dose from 11:00 AM through 5:00 PM at time points consistent with each patient's usual levodopa dosing. The "scheduled levodopa dose" is defined as the afternoon levodopa dose prior to which the UPDRS assessment is performed and after which the UDysRS Parts 3+4 assessment is performed. The second study treatment dose should be taken 0 to 120 minutes BEFORE the "scheduled levodopa dose" (NOT after). A consistent effort will be made to ensure that all study visits for an individual patient will occur at approximately the same time of the day. The same in-clinic procedural timing will be kept as best as possible for all visits for each patient. Every effort should be made to ensure that, for a given efficacy assessment, all measurements are performed by the same rater for each individual patient for all visits.

An in-clinic assessment of dyskinesia according to UDysRS will be conducted by the study rater at the time points noted in the schedule of assessments ([Table 4](#)). At Baseline (Visit 2), all UDysRS parts (Parts 1 to 4) must be assessed before the initial study treatment dose (refer to [Appendix 13.1](#)). For the rest of the time points, UDysRS must be assessed as per the in-clinic visit procedural flow in [Appendix 13.2](#). The historical parts of the UDysRS (Parts 1 and 2) will be performed at any time during the visit (at Baseline [Visit 2], at any time before the initial study treatment dose). The objective score (Parts 3 and 4) will be performed at least 30 minutes following the patient's in-clinic dose of levodopa (the "scheduled levodopa dose"), at a time when the patients are normally in an "ON" state and experiencing their peak dose dyskinesia.

Patients will complete an "ON/OFF" home diary for 3 consecutive days before the in-clinic visit at the time points noted in the schedule of assessments ([Table 4](#)). The patients will record their motor state ("OFF", "ON with no dyskinesia", "ON with no troublesome dyskinesia", "ON with troublesome dyskinesia", and "asleep") every 30 minutes during the 24-hour period. During this period, patients will also record their anti-PD and study treatment doses. A phone call will be made 4 days before each of these in-clinic visits to remind patients to complete their "ON/OFF" home diaries and bring them to the clinic.

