Visit #	Visit 1	Visit 1.1 ^{gg}	Visit 2 ^e	Visit 3 ^{ee}	Visit 4 ^{ee}	Visit 5 ^{ee}	Visit 6 ^{ee}	Visit 7 ^{ee}	TC	Visit 8	
Study Visit Day (window)	-63 days ^{ff}	-21 days (none)	1 (none)	29 (±1 day)	43 (±1 day)	70 (±1 day)	91 (±1 day)	112 (±1 day)	119 (none)	126 (±1 day)	
Study Phone Call Day			7, 14, 21, ^f	25 ^g	52 ^g	73 ^g	94 ^g		114, 116 ^h		
Visit Descriptor	SCR	SCR	BSL	Safety	Efficacy ⁱ Safety PK	Efficacy ⁱ Safety	Efficacy ⁱ Safety PK	Efficacy ⁱ Safety PK	Phone call	Final Safety Follow-up	
Informed consent	X										
Randomization to treatment groups			X								
Inclusion/ Exclusion criteria	X		X								
MMSE	X										
Demographic data	X										
Psychiatric history	X										
Medication history ^j	X										
Alcohol/ illicit drug use inquiry	X										
Hoehn and Yahr scale	X										
Training on recognizing motor sates and diary documentation ^k	X ^{hh}	X									
Motor state concordance testing ^l	X ^{hh}	X									
“ON/OFF” Home diaries dispensing	X ^{hh}	X		X	X	X	X				

Study Period ^a	Screening		Treatment Period						Down-titration	Safety Follow-Up
			Up-titration	Maintenance						
Study Week			Week 1 ^b	Week 5	Week 7	Week 10	Week 13	Week 16/ET ^c	Week 17 ^d	Week 18
Visit #	Visit 1	Visit 1.1 ^{gg}	Visit 2 ^e	Visit 3 ^{ee}	Visit 4 ^{ee}	Visit 5 ^{ee}	Visit 6 ^{ee}	Visit 7 ^{ee}	TC	Visit 8
Study Visit Day (window)	-63 days ^{ff}	-21 days (none)	1 (none)	29 (±1 day)	43 (±1 day)	70 (±1 day)	91 (±1 day)	112 (±1 day)	119 (none)	126 (±1 day)
Study Phone Call Day			7, 14, 21, ^f	25 ^g	52 ^g	73 ^g	94 ^g		114, 116 ^h	
Visit Descriptor	SCR	SCR	BSL	Safety	Efficacy ⁱ Safety PK	Efficacy ⁱ Safety	Efficacy ⁱ Safety PK	Efficacy ⁱ Safety PK	Phone call	Final Safety Follow-up
“ON/OFF” Home diaries assessments			X ^m		X ^g	X ^g	X ^g	X ^g		
Prior and concomitant medications review ⁿ	X		X	X	X	X	X	X	X	X
Physical examination	X		X ^o					X ^p		X ^p
Vital signs ^q	X		X	X	X	X	X	X		X
Neurological examination	X ^{hh}	X	X ^o					X ^p		X ^p
Body weight and height ^r	X		X	X	X	X	X	X		X
Clinical laboratory tests (Serum haematology and biochemistry) ^s	X		X	X	X	X	X	X		X
Urinalysis (dip stick)	X		X	X	X	X	X	X		X
Serum pregnancy test (if applicable) ^t	X									
Urine pregnancy test (if applicable) ^u			X	X	X	X	X	X		X
ECG (12-lead) Consecutive triplicate of 10 seconds ^v	X		X	X	X	X	X	X		X
C-SSRS	X ^{hh}	X	X	X	X	X	X	X		X
QUIP-RS	X ^{hh}	X	X	X	X	X	X	X		X

Study Period ^a	Screening		Treatment Period						Down-titration	Safety Follow-Up
			Up-titration	Maintenance						

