- c. An early termination (ET) visit should be performed for patients who discontinue prematurely within 1 week of ET.
- d. Down-titration period. At the end of the maintenance period or at ET, active treatment patients will undergo a down-titration- period in which they will receive pridopidine 75 mg BID on Days 1 to 2 followed by pridopidine 75 mg QD on Days 3 to 4 of Week 17. Patients randomly assigned to the placebo arm will receive matching placebo at the same dosing schedule as patients assigned to the active treatments. Refer to [Section 5.2](#).
- e. All efficacy and safety measures, except the ECG after the second study treatment dose must be assessed before the first study treatment dose. Refer to the in-visit procedural flow for Baseline (Visit 2) in [Appendix 13.1](#).
- f. Telephone contacts will be conducted on Day 1 of Week 1-4 (up-titration period) to remind patients to up-titrate their dosage and ask them to provide details on AEs and concomitant medication changes.
- g. Patients will be called 4 days before each of the relevant visits to remind them to complete the "ON/OFF" home diary every 30 minutes during the 3 consecutive days before the visit and to bring them to the clinic.
- h. Telephone contacts will be conducted on Days 2 and 4 of Week 17 to remind patients to down-titrate and discontinue the dosing.
- i. Onsite/in-clinic assessments will be scheduled around the second (PM) study daily treatment dose from 11:00 AM through 5:00 PM and will use time points consistent with each patient's usual levodopa dosing. On clinic visit days, the "scheduled levodopa dose" is defined as the in-clinic afternoon levodopa dose prior to which the UPDRS assessment is performed and after which the UDysRS parts 3+4 assessment is performed. The study treatment afternoon dose should be taken 0 to 120 minutes BEFORE the "scheduled levodopa dose" (NOT after). As much as possible, all study visits for an individual patient will occur at approximately the same time of the day. The same in-clinic procedural timing will be kept for all visits for each patient.

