### 6.2.1 ON time without troublesome dyskinesia and other endpoints based on “ON/OFF” home diary

Mean actual value and mean change from Baseline (Visit 2) to all post-baseline visits in ON time without troublesome dyskinesia based on “ON/OFF” home diary completed by the subjects during 3 consecutive 24 hour intervals will be evaluated as a secondary endpoint. The daily ON time without troublesome dyskinesia is defined as the sum of daily ON time without dyskinesia and daily ON time with non-troublesome dyskinesia.

This endpoint will be presented both as daily ON time without troublesome dyskinesia during waking hours and as total number of hours with ON time without troublesome dyskinesia, normalized to a 16-hour waking day.

The Baseline is defined as the home diary obtained on 3 consecutive days prior to the Baseline visit (Visit 2). The diaries collected during the Maintenance Period, on 3 consecutive days prior to Visit 4 (Week 5/7), Visit 5 (Week 8/10), Visit 6 (Week 11/13) and Visit 7 (Week 14/16) will be used as response variables. In case of missing or non-valid diary days during the 3 consecutive days prior to the visits during the Maintenance Period, the last 3 recorded days between Visits 3-4 (for Visit 4), 4-5 (for Visit 5), 5-6 (for Visit 6) and 6-7 (for Visit 7), but no more than 7 days before the visit with non-missing and valid diary data will be used instead. In case of missing or non-valid diary days before Baseline, the 3 last non-missing and valid diary days prior to the first dose of study drug will be used regardless of time between the day when the diary was completed and the Baseline visit.

The validity of the diary entries will be checked prior to including a diary day in the summary calculations. Only valid diary days will be included in the diary summarizations. The diary endpoints will be derived as defined below.

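### Protocol Table 4 puts the diary-reminder calls 18 days before the diary visits, while its own footnote g and Section 3.1.4 require 4 days

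*Protocol*

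**What the plan says.** Two places in the protocol set the timing of the reminder in words, and they agree. Section 3.1.4 (Efficacy) states: "A phone call will be made 4 days before each of these in-clinic visits to remind patients to complete their" diaries. Footnote g of Table 4 (Schedule of Assessments, Section 6) states: "Patients will be called 4 days before each of the relevant visits to remind them". The footnote goes on to say what the caller asks for: entries in the "home diary every 30 minutes during the 3 consecutive days before the visit and to bring them to the clinic".

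Table 4 also gives the timing in numbers. The row headed "Study Phone Call Day" prints Days 25, 52, 73 and 94, each marked with footnote g. The diary-assessment row carries the same footnote at Visits 4, 5, 6 and 7, which the table places on Days 43, 70, 91 and 112, each ±1 day. Visit 3 (Day 29) has no diary assessment, but it is the first post-baseline visit at which diaries are dispensed. Diaries are also handed out at screening, for the baseline record.

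SAP 6.2.1 takes its response data from diaries kept "on 3 consecutive days prior to Visit 4 (Week 5/7), Visit 5 (Week 8/10), Visit 6 (Week 11/13) and Visit 7 (Week 14/16"). If those days are missing or invalid, it substitutes the last 3 recorded days between the two visits, "but no more than 7 days before the visit with non-missing and valid diary data will be used instead".

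**The concern.** The row and its own footnote cannot both be followed. A site that works from the printed day numbers makes the call about two and a half weeks before the visit. A site that works from the footnote makes it 4 days before.

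The purpose of the call is to obtain entries on 3 specific days. The diary supplies ON time without troublesome dyskinesia (listed first among the secondary endpoints in Protocol 7.2), ON time without any dyskinesia, OFF time, and the OFF-time half of the responder definition. Under SAP 6.2.1 a visit with only one valid diary day is treated as missing. Under SAP 6.2.4 a visit without OFF time has no responder status, except in the sensitivity analysis that counts missing data as non-improvement. What is at stake is therefore the completeness of several secondary endpoints. The primary endpoint, a UDysRS sum, uses no diary data.

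**Working it through.** **Inputs.** Call days 25, 52, 73, 94 and visit days 43, 70, 91, 112 (±1) come from Protocol Table 4. The stated lead of 4 days comes from footnote g and Section 3.1.4. The version 1.1 visit days 29, 56, 77, 98 (Visits 4 to 7) come from the first design figure in SAP 4.1. Post-baseline diary dispensing at Visits 3 to 6 (Days 29, 43, 70, 91) comes from Table 4.

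**Step 1: lead time = visit day − call day.**

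| Diary visit | Visit day | Printed call day | Lead (days) | Call day for a 4-day lead | Version 1.1 visit day | Lead under version 1.1 |
|---|---|---|---|---|---|---|
| 4 | 43 | 25 | 18 | 39 | 29 | 4 |
| 5 | 70 | 52 | 18 | 66 | 56 | 4 |
| 6 | 91 | 73 | 18 | 87 | 77 | 4 |
| 7 | 112 | 94 | 18 | 108 | 98 | 4 |

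The stated 4 days is not reproduced at any visit of the current schedule. The lead is 18 days, or 17 to 19 with the visit window, and each call is 18 − 4 = 14 days early. The version 1.1 visit days reproduce 4 days at all four visits.

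**Step 2: could the row belong to other visits?** Matched to the columns in which the numbers stand (Visits 3 to 6), visit day − call day is 29 − 25 = 4, 43 − 52 = −9, 70 − 73 = −3 and 91 − 94 = −3. Only Visit 3 fits, and it has no diary assessment. This reading does not rescue the row.

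**Step 3: was the rest of the row updated?** Yes. Its last entries, Days 114 and 116, are Days 2 and 4 of Week 17 (Week 17 begins on Day 113), as footnote h requires under the current schedule.

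**Step 4: order of call and dispensing (call day − dispensing day).** 25 − 29 = −4, 52 − 43 = 9, 73 − 70 = 3, 94 − 91 = 3. Only the first call precedes the post-baseline dispensing for its visit. With a 4-day lead the differences are 39 − 29 = 10, 66 − 43 = 23, 87 − 70 = 17 and 108 − 91 = 17, all positive.

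**Step 5: what if a patient filled in the diary straight after the call?** The 3 days after the call lie 18 − 1 = 17, 18 − 2 = 16 and 18 − 3 = 15 days before the visit. With the ±1 day window the extremes are 14 and 18. All are beyond the 7 days that the SAP fallback allows. For Visit 4 the entries would be on Days 26 to 28, which is also before Visit 3 and so outside the Visit 3 to 4 interval that the SAP specifies. This step is conditional: it assumes behaviour that the call does not ask for.

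**The case against.** A reader might infer that reminded diaries necessarily fall outside the SAP window, so that a patient called on the listed day loses that visit's data. The documents do not support this. The call asks for the 3 days before the visit, and a patient who remembers that instruction records usable days however early the call comes. The 7-day limit is a fallback for missing or invalid days, not the main diary window, and two valid days are enough for a visit to count. The dispensing point is also limited. Diaries had already been given out at screening, and the diary for Visit 4 is handed over on Day 29, 43 − 29 = 14 days before that visit, so the patient is not without one on the days that matter.

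Three further points weigh against a high rating. Each wrong number carries the footnote that states the 4-day rule, so an attentive site could notice the conflict. The stakes have fallen: the SAP supersedes the protocol, reports that the trial stopped before 30 subjects were enrolled (9.3), applies no multiplicity adjustment and treats p-values as mainly descriptive (9.4). And the printed days suit the version 1.1 visit days, so they need not have misled anyone on that schedule.

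All of this stands, and it limits the consequence. None of it removes the contradiction, which is in the current operating table and repeats at every diary visit.

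**Conclusion.** Wrong as written, minor severity. The size of the error is certain: 18 days instead of 4 at all four diary visits, a uniform shift of 14 days. That the numbers were carried over from version 1.1 is an inference. The exact match at four visits and the two-week lengthening of titration make it probable, but the version 1.1 schedule table is not among the documents.

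The supportable consequence is a reminder that does its job less well. It comes too early to prompt entries on the right 3 days, and the first call comes before the diary for that visit has been dispensed. Entries made straight after the call would be unusable under the SAP fallback. The documents give no basis for saying how often that would happen or how many visits would be missing. No sample-size or power figure is affected.

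**What to change.** Reconcile the call-day row of Protocol Table 4 with footnote g and Section 3.1.4. If the 4-day lead is what was intended, the days become 39, 66, 87 and 108. That changes four numbers in one row (repeated on each page of the table) and touches no endpoint or analysis. Because the SAP describes the study as still ongoing when it was written, it is also worth checking which call days sites used for patients on the version 2.0 schedule before interpreting missing or mistimed diaries. This needs only a query to the sites.

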6.1 Study Visits

The schedule of assessments by study visit is presented in [Table 4](#). Detailed instructions for the conduct of study assessments and procedures will be provided in the study manual provided to investigators.

6.2 Efficacy Assessments

Every effort should be made to ensure that, for a given efficacy assessment, all measurements are performed by the same rater for each individual patient for all visits.

6.2.1 UDysRS

The UDysRS is designed to evaluate involuntary movements often associated with treated PD. The scale comprises two primary sections:

- Historical [Part 1 (ON-Dyskinesia) and Part 2 (OFF-Dystonia)]
- Objective [Part 3 (Impairment) and Part 4 (Disability)]

ON-Dyskinesia refers to the choreic and dystonic movements described to the patient as “jerking or twisting movements that occur when your medicine is working.” OFF-Dystonia should be described to the patient as “spasms or cramps that can be painful and occur when your Parkinson’s disease medications are not taken or are not working”. The assessments will be carried out at the time points noted in the schedule of assessments ([Table 4](#)). Every effort should be made to ensure that all UDysRS assessments are performed by the same rater for each individual patient.

6.2.2 UPDRS

The UPDRS scale is divided into 4 parts. Part 1 is designed to rate mentation, behavior and mood (questions 1 to 4). It is to be collected as historical information without direct relevance to “ON” or “OFF” periods experienced by the patient. Part 2 (questions 5 to 17) is designed to rate activities of daily living for both “ON” and “OFF” periods. Part 3 (questions 18 to 31) is done as a motor examination at the time of a visit. Part 4 (questions 32 to 42) is historical information designed to rate complications of therapy. The various items to be rated are scored using a 5-point system (i.e., 0 is normal and 4 indicates a severe abnormality). UPDRS Part 2 and Part 3 will be measured at the time points noted in the schedule of assessments ([Table 4](#)).

6.2.3 “ON/OFF” Home Diary Assessments

The “ON/OFF” home diary assessments are assessed during three consecutive 24-hour periods. During the screening period, potential patients and any involved caregivers or study partners if applicable will be trained to recognize the different motor states (“ON without dyskinesia,” “ON with no troublesome dyskinesia,” “ON with troublesome dyskinesia,” and “OFF”), and to complete a corresponding “ON/OFF” home diary. Training will be conducted by a well-

trained rater. After training, the patients will be invited to the clinic; the study rater and the patients will complete an “ON/OFF” diary at half-hour intervals over a 4-hour period to ensure concordance of >75% between the evaluations (e.g., “ON, OFF and dyskinesia”) of the rater and the patient. After assurance of >75% concordance between the rater and patient, the patients will complete at their homes the “ON/OFF Home Diary” during three consecutive 24-hour periods (72 hours total). The patients will send the completed diaries to the site (e.g., via fax, email) during the first two weeks of the screening period because these diaries will serve as the baseline motor home diary and for eligibility to participate in the study. Training may be repeated during the screening period to ensure concordance with investigator ratings. The assessments will be carried out at the time points noted in the schedule of assessments ([Table 4](#)).

